Aware Treatment: Aware Recovery Care (ARC) is an in-home addiction treatment program that provides highly intensive, rigorously monitored, 52 weeks of intensive outpatient care, based on a chronic disease model of care. The approach implements principles of evidence-based practices including Motivational Interviewing, Cognitive Behavioral Therapy, and Dialectical Behavioral Therapy. Additionally, all families are offered education and the opportunity to participate in the treatment process. The client's individualized treatment team consists of a licensed professional (nurse or master's level clinician), two Certified Recovery Advisors (CRAs), and an LMFT. The clients care team is overseen by a master's level alcohol and drug counselor, an advanced practicing nurse, and an addiction psychiatrist. The licensed professional is responsible for leading the team, collaborating with external providers, communicating with family members and providing referrals to external providers as needed. The CRAs are lived-experience advisors, at least one of whom is both age and gendered match in order to provide a more intimate therapeutic relationship. CRAs are responsible for delivering a staged biopsychosocial curriculum. Familial involvement is another key component of this model, with education and frequent communication provided. All care teams include a Licensed Marriage and Family Therapist for 6 family therapy sessions, as well as 4 family education sessions delivered by a special trained family education facilitator.

Randomization. At the randomization visit, the research assistant will conduct assessments to evaluate alcohol use. Eligible patients will be assigned to one of the two groups using randomization sequence. The randomization sequence will allow for equal representation between two groups without bias on gender, age or ethnicity given all individuals will be categorized as single variable

Assessments:

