- F. Describe the provisions for protection of participant privacy Write here
- G. Describe the methods for the security of storage and sharing of materials Write here
- 6. **Subject Population:** Provide a detailed description of the types of human subjects who will be recruited into this study.
 - We will recruit 110 individuals with alcohol use disorder as diagnosed by the DSM-5. They will be recruited at Aware Recovery Center in North Haven, CT.

7.	Subject classification: Check off all classifications of subjects that will be specifically recruited for enrollment in
	the research project. Will subjects who may require additional safeguards or other considerations be enrolled
	in the study? If so, identify the population of subjects requiring special safeguards and provide a justification
	for their involvement.

for their involvement.	the population of subjects requir	ing special safegualus and provide a justification
⊐Children	☐ Healthy	□Fetal material, placenta, or dead fetus

APPROVED BY THE YALE UNIVERSITY IRB 6/9/2020

IRB# 2000027787

□Non-English Speaking	☐ Prisoners	☐Economically disadvantaged persons
□Decisionally Impaired	☐ Employees	☐Pregnant women and/or fetuses
□Yale Students	☐ Females of childbearing pote	ntial
NOTE: Is this research proposal o	designed to enroll children who a	are wards of the state as potential subjects?

8. Inclusion/Exclusion Criteria: What are the criteria used to determine subject inclusion or exclusion? Inclusion Criteria: 1) are at least 21 years old, 2) currently enrolled at Aware In home treatment, and 3) Primary or secondary DSM-5 diagnosis of alcoholism use disorder (AUD).

Exclusion Criteria: 1) Current suicide or homicide risk, 2) meet criteria for DSM-IV current psychotic disorder, or bipolar disorder, 3) does not have phone access with text message capabilities, 4) Unable to read or understand English, 5) Unable to complete the study because of anticipated incarceration or move, 6) Life-threatening or unstable medical problems, 7) No course of current or pending legal action, 8) Soberlink results being used for child custody or legal circumstance.

- 9. How will **eligibility** be determined, and by whom?

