13. **Statistical Considerations:** Describe the statistical analyses that support the study design. A sample size of 110 would provide >80% power (α = .05) to detect a medium to large effect size (d= .65) and allow to fully evaluate gender differences. Greater power is provided by the repeated measures GEE and LMM analysis for the primary outcomes of BAC screen negative for alcohol drugs and days/month of self-reported illicit drug use. Sample size calculations for LMM are dependent on the number of repeated events, the retention rate, and the interclass correlation, in addition to the alpha level, the expected effect size, and the statistical power 198. The current randomized trial would provide estimates to guide a power analysis for a large Stage II study. Statistical procedures and models for analyzing data have been selected according to the research hypotheses being investigated and the types of data available. We will use α < .05, but will use appropriate corrections for multiple tests. Statistical analyses will be conducted on an intention-to-treat sample using SPSS. Using chi square and t-tests, we will first conduct preliminary analyses of the adequacy of the randomization procedure, the comparability of baseline measures for the two groups, and the possible need for covariates in the analyses of treatment outcome data.

SECTION II: RESEARCH INVOLVING DRUGS, BIOLOGICS, RADIOTRACERS, PLACEBOS AND DEVICES

ft
his
section
(or one
of its part
s. A or B
() is not
applicable.
check o
ff N/A
and de
lete the
rest of th
e section.

A.	RADIOTRACERS ⊠N/A	
1.	Name of the radiotracer: Write here	
2.	Is the radiotracer FDA approved? □YES	□NO

- If NO, an FDA issued IND is required for the investigational use unless RDRC assumes oversight.
- 4. **Background Information:** Provide a description of previous human use, known risks, and data addressing dosage(s), interval(s), route(s) of administration, and any other factors that might influence risks. If this is the first time this radiotracer is being administered to humans, include relevant data on animal models.

Check one: □IND# Write here or □RDRC oversight (RDRC approval will be required prior to use)

Write here

3.

4. **Source:** Identify the source of the radiotracer to be used. *Write here*

5. **Storage, Preparation and Use:** Describe the method of storage, preparation, stability information, method of sterilization and method of testing sterility and pyrogenicity.

Write here

R	DRUGS/BIOLOGICS

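### Unstratified allocation balances gender, age and ethnicity only on average; stratifying by gender and prespecifying a gender term would be a cheap, modest improvement

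*Combined protocol and SAP*

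**What the plan says.** The Randomization paragraph in Section I, 4 (Research Plan) states: "Eligible patients will be assigned to one of the two groups using randomization sequence". It then says that the sequence will allow "equal representation between two groups without bias on gender, age or ethnicity given all individuals will be categorized as single variable". The readable text names no strata, block size or minimisation. The Procedure text in the same section gives a web address for a randomiser and the two conditions.

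Section I, 13 (Statistical Considerations) says that the sample size will "allow to fully evaluate gender differences". It plans chi-square and t-tests of whether randomisation worked, of "the comparability of baseline measures for the two groups, and the possible need for covariates in the analyses of treatment outcome data". No covariate is named in advance.

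The expected proportion of women is not given anywhere. Section I, 4 only lists the sample's gender make-up among the items that automatic reports may track.

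**The concern.** The reason offered does not support the property claimed. Treating all participants as one category is the absence of stratification. It ensures that gender, age and ethnicity play no part in who gets which arm, so any imbalance is due to chance. It does not ensure that the two arms of a single 110-person trial have a similar mix.

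Gender matters most here, because it is the one baseline trait that the plan singles out for analysis. An imbalance on gender costs some precision in the gender-adjusted arm comparison and in comparisons within each gender. The plan's remedy is to look at baseline tests and then decide on covariates. That makes the outcome model depend on the observed baseline data, and a non-significant baseline test does not show that a covariate is unimportant to the outcome. Fixing the term in advance is the stronger method.

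**Working it through.** **Inputs from the plan.** N = 110: "We will recruit 110 individuals with alcohol use disorder as diagnosed by the DSM-5" (Section I, 6). Section I, 13: "A sample size of 110 would provide >80% power (α = .05") and "to detect a medium to large effect size (d= .65").

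**Assumptions.** 1:1 allocation (55 per arm), a two-sided test, and 30-50% women, that is k = 33, 44 or 55 of 110.

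**Step 1: the plan's own figure.** Power = Φ(d·√(n/2) − 1.96) = Φ(0.65·√27.5 − 1.96) = Φ(3.409 − 1.96) = 92.6% (92.2% by the t distribution). This agrees with the plan's statement of more than 80%. Stratification does not change N.

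**Step 2: chance imbalance with equal, unstratified arms.** The number of women w in one arm is hypergeometric (110 people, k women, 55 drawn). The difference in the share of women is D = (2w − k)/55, with SD = (2/55)·√[k(110 − k)/436].

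| Women | k | SD of D (points) | P(10 points or more) | P(15 or more) | P(20 or more) |
|---|---|---|---|---|---|
| 30% | 33 | 8.8 | 0.21 | 0.10 | 0.04 |
| 40% | 44 | 9.4 | 0.33 | 0.08 | 0.03 |
| 50% | 55 | 9.6 | 0.25 | 0.13 | 0.06 |

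The probabilities do not rise steadily with k because D moves in steps of 2/55 = 3.6 points. For k = 44 the first value at or above 10 is 10.9 points; for k = 33 and 55 it is 12.7. At 20% women the chance of 10 points or more is 0.23.

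**Step 3: simple randomisation instead (arm sizes free to vary).** By simulation, the chance of 10 points or more is 0.25, 0.29 and 0.29 at 30%, 40% and 50% women. If there is no blocking, one arm's size has a 95% range of 45-65 (binomial, 110 and 0.5).

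**Step 4: what an imbalance costs.** In a gender-adjusted comparison of equal arms, the variance is multiplied by 1/(1 − φ²), with φ² = D²/[4p(1 − p)] and p the share of women.
- D = 10 points: φ² = 0.01/0.84 = 0.012 at p = 0.3, and 0.010 at p = 0.5. Inflation is about 1%.
- D = 20 points: φ² = 0.04/0.84 = 0.048 at p = 0.3, and 0.040 at p = 0.5. Inflation is 5.0% and 4.2%.
- Averaged over all allocations, φ² = Var(D)/[4p(1 − p)] = 1/109, or about 0.9%.
- A 45/65 split costs 110²/(4 × 45 × 65) = 1.034, or 3.4%.

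With 5% inflation, power at d = 0.65 becomes Φ(3.409/√1.05 − 1.96) = Φ(1.367) = 91.4%, against 92.6%.

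Without adjustment, an illustrative gender effect of 0.3 SD (an assumption) with a 10-20 point imbalance shifts the arm difference by 0.3 × 0.10 = 0.03 to 0.3 × 0.20 = 0.06 SD.

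**Step 5: with gender-stratified blocks.** Using blocks of 4 (an assumption) at 30% and 50% women, the largest simulated difference was about 2 points, and none reached 10.

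**Step 6: the gender analysis itself.** At d = 0.65, power within women alone is 44%, 56% and 66% at 30%, 40% and 50% women. Power for a gender-by-arm interaction of 0.65 SD is 35%, 39% and 40%. These figures already assume perfect balance, so stratifying cannot raise them.

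**The case against.** A reader might infer that the plan guarantees arms matched on gender, age and ethnicity, and that this guarantee is false. The text does not go that far. Equal representation can mean equal arm sizes, and freedom from bias on these traits can mean that allocation ignores them, which is true of an unstratified sequence. The planned baseline tests also show that the authors do not treat balance as assured. This stands. What remains is that the sentence offers the single category as the reason for equal representation, and many readers would take that to mean balanced composition.

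A reader might also infer a threat to validity. There is none: unstratified 1:1 randomisation is legitimate, and the losses in Step 4 are too small to alter the power conclusion.

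It would be tempting to present stratification as the way to deliver the gender analysis. It is not. The obstacle there is subgroup size.

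Nor do the documents show that blocking is absent. The readable Procedure text begins partway through a sentence, at the web address, so a description of blocking may be lost. The 45-65 range therefore applies only if allocation is unblocked.

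Finally, the plan does handle imbalance, through its baseline tests and possible covariates. That is a partial answer, weaker than a term fixed in advance.

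**Conclusion.** The point holds in a limited form. The stated reason does not support balanced composition in a single trial. With equal arms and an assumed 30-50% women, a gender difference of 10 points or more has a probability of about 21-33%, and one of 15 points or more about 8-13%. Gender is a declared analysis factor, so stratifying on it and fixing it in the models is a better method than choosing covariates after baseline tests.

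The gain is modest: about 1-5% of variance in trials where a 10-20 point imbalance occurs, and about 1% on average. Severity is minor, and the change is a cheap improvement. The figures rest on 1:1 allocation, the assumed gender split, and the readable text being complete on strata.

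**What to change.** - In the Randomization paragraph, state that allocation is 1:1 in permuted blocks of varying size, stratified by gender, for example with one list per gender.
- Replace the balance sentence with one saying that allocation does not depend on age or ethnicity, and that these are balanced in expectation only.
- In Section I, 13, prespecify gender as a fixed term in the GEE and LMM models, whatever the baseline tests show.

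**Cost.** No extra participants or staff; minor list set-up and one model term. The documents do not show whether the web tool supports strata. Preparing a separate list for each gender should avoid the need for that feature.

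These changes do not make the gender-difference analysis adequately powered, and the plan should not suggest that they do.

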Patients assigned to the Soberlink-Aware condition will receive a 30-minute orientation to the Soberlink, including an initial their first administration of the BAU. Participants will learn the following:

- 1. The Soberlink System consists of a wireless Breathalyzer that uses a professional grade fuel cell sensor to detect alcohol levels at an accuracy of +/-.005 BAC.
- 2. The device also has an embedded camera and uses Facial Recognition software to automatically identify the client at the end of the test.
- 3. The participant will have a set testing schedule that consists of a minimum of 2 tests per day. The participant will have a test window of 2 hours with a Late window of 1 hour.
- 4. When the participant blows into the Soberlink device, it will capture the BAC level while the embedded camera takes a photo of the participant during the test

The breathalyzer device uses fuel cell technology to detect BAC, is handheld, and includes an embedded camera. It uses wireless technology to send the data in real-time. The cloud-based monitoring system includes a scheduler that automatically tracks scheduled tests and sends reminders to the client for testing. Retesting is automatically scheduled if a positive test is received or if a client's identity cannot be verified. The device locks out for 15 minutes to ensure alcohol evaporates before the next test. Facial Recognition software ensures identity is

IRB# 2000027787

approved or declined in real-time. Artificial intelligence is used to report on testing and Green, Yellow and Red visual icons are used in all reporting to identify events.

All individuals in group 1 will be required to complete two BAC's per day. A testing window will be scheduled with each individual between 7am to 9am (morning BAC) and 8pm to 10pm (evening BAC). During the testing window, all individual in this group can provide the BAC at any time within the window, all tests performed outside the window will be recorded but counted as unscheduled test on the BAC spreadsheet. All participants can opt in to receive a text-reminder sent by Soberlink's automated server to remind the patient about their morning and evening BACs.

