Individuals who miss two consecutive BAC's will be followed up by either Research Assistant or the PI. Individuals who miss four consecutive BAC's without contact of the PI or the research assistant will be temporarily hold unless the individual has expressed thoughts of leaving the study prematurely. Missing more than six consecutive BACs without communication will result in termination from the study by the PI. A pilot study contacted at Aware prior to the PI being involved demonstrated little reactivity or premature departure for those who had access to the Soberlink device.

Aware/Group 2:

This group will not receive access or training to Soberlink device, however they will be recruited to complete the same set of surveys at the same time intervals (See Figure 2). Upon completion of the surveys, the participants in group 2 will be paid, and told reminded the subsequent follow-ups. Reminder emails (see attached reminder emails) will be sent out the day before, and the day of the 1 month, 2 month and 3 month evaluations. Subsequent phone calls will be made by the research assistant to the participant if they have missed their evaluation. The estimated time of the process will take under 30 minutes to complete.

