We are planning to assess a broad range of subject characteristics, process measures and treatment outcomes over the 3-month trial and at the 6 week post treatment follow-up (See Table 1). Baseline assessments are designed to ensure that patients meet eligibility criteria and that important predictor variables such as cognitive impairment are assessed. Baseline measures include evaluation and understanding of the extent of the AUD issue from a several different vantages points. Primary outcome measures include reductions in days per week of use and negative BAU screens for alcohol. Monthly assessments will take approximately 30 minutes and monthly and follow-up's 45 minutes. Patients will be paid \$10 for the baseline and monthly assessments, \$25 for follow-up assessments (up to \$65 total).

active alcohol use disorders.

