Table 1. List of Assessments Screening & Baseline Assessments a) Generalized Anxiety Disorder (GAD-7) will be used to assess for generalized anxiety The Structured Clinical Interview for DSM-V (SCID) will be used to assess lifetime and current DSM- V substance use and Axis I and II psychiatric disorders ¹⁸¹ and screen patients for psychiatric eligibility. c) Patient Health Questionnaire (PHQ-9) will be used for depression symptoms for the past 2 weeks. d) Substance Use History will assess frequency, intensity and duration of use and route of administration of drugs. e) Alcohol Abstinence Self-Efficacy Scale will evaluate the participant's beliefs of alcohol usage. Outcome Measures. a) Soberlink (BAC): sensor to detect alcohol levels at an accuracy of +/-.005 BAC. BAC is established by the manufacturer based on predetermined cut off points b) The Time Line Follow Back (TLFB), administered by research administer onto a secure webserver. Will be used to collect self-reported frequency, quantity and route of administration of prescription opioids, cocaine, alcohol and other drugs use during the preceding 30 days, and use 185-187 Quality of Life Scale is a self-directed survey that assess the quality of life of the individual. d) Soberlink Use Survey is a self-directed survey that evaluates the effectiveness of the device. e) The Drug Risk Response Test (DRRT) ^{189,190} is a role-playing assessment of coping responses to drug use risk situations, and takes 8-10 minutes to complete. The instrument is composed of six audio-taped scenarios. Patients are instructed to imagine that they are in the situation and provide a detailed account to how they would respond to that situation. Patient accounts are recorded and scored by trained evaluators. The instrument provides 4 measures: the number of coping responses, the number of activities per response, the quality of the best response and the

Data monitoring procedures involve an organizational structure of clearly defined tasks assigned to all research personnel involved in the conduct of this study. The organizational structure used to ensure quality of data in this project include: 1) extensive training and close supervision of research assistants in data collection;

f) AUDIT C- is brief alcohol screen that reliably identifies patients who are hazardous drinkers or have

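### Negative breath-alcohol screens are a primary outcome but are collected only in the device arm, so no randomised comparison on them is possible

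*Combined protocol and SAP*

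**What the plan says.** - **Primary outcomes.** Section I.4, Assessments: "Primary outcome measures include reductions in days per week of use and negative BAU screens for alcohol". Section I.13 again names two primary outcomes and attaches the model to them: "Greater power is provided by the repeated measures GEE and LMM analysis for the primary outcomes of BAC screen negative for alcohol drugs", with the second given as "days/month of self-reported illicit drug use".
- **Source of the screen.** Under Outcome Measures, Table 1 lists "Soberlink (BAC): sensor to detect alcohol levels at an accuracy of +/-.005 BAC". It lists no other breath, urine or blood test for alcohol. The term BAU in the Assessments text is the same test: the Soberlink orientation, given only to the device arm, is described as "including an initial their first administration of the BAU".
- **Who is tested.** Section I.4 requires two breath tests a day from Group 1. Of Group 2 it says: "This group will not receive access or training to Soberlink device". Group 2 completes the same surveys at the same times. Section V supplies the device and service to the Soberlink arm only.
- **What the trial is for.** Aim 1 in Section I.1 is whether Soberlink increases abstinence. Section I.13 promises an intention-to-treat analysis, a sample size based on a standardised difference d, and corrections for multiple tests by a method it does not name.

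**The concern.** The breath reading is both the intervention and a primary outcome. Group 2 is never scheduled to produce one. This is not missing data in the usual sense: no Group 2 value is ever observed, so no model can recover the contrast, and any imputation (all negative, all positive, or borrowed from Group 1) would set the answer by assumption.

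A high share of negative screens in Group 1 says nothing about whether the device raised abstinence, because nothing shows what the share would have been without it. With the outcome labelled primary, a single-arm rate could be read as a randomised result. Section I.13 also wants this trial to supply estimates for powering a larger Stage II study, and it can supply no between-arm estimate for this outcome.

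**Working it through.** **Inputs.** Total N = 110, alpha = .05, d = 0.65 and power above 80% (Section I.13). Allocation is equal: "The randomization sequence will allow for equal representation between two groups" (Section I.4, Randomization), so 55 per arm is inferred. Two tests a day in Group 1 and none in Group 2 (Section I.4). Assumptions: two-sided testing, since sidedness is not stated, and a three-month period of 84 to 91 days.

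**1. The plan's own power figure.** Normal approximation for two means:

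power = Φ(d·√(n/2) − z) = Φ(0.65 × √27.5 − 1.96) = Φ(3.409 − 1.960) = Φ(1.449) = 0.926.

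The t-test version gives 0.922, and a one-sided test gives 0.961. The n for 80% power is 2 × (1.960 + 0.842)² / 0.65² = 37.2, so 38 per arm (39 by t-test). The stated figure is reproduced, for an outcome observed in both arms.

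**2. Observations available for the breath-screen outcome.**

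| | Group 1 | Group 2 |
|---|---|---|
| Scheduled tests, 84 days | 55 × 2 × 84 = 9,240 | 0 |
| Scheduled tests, 90 days | 55 × 2 × 90 = 9,900 | 0 |
| Scheduled tests, 91 days | 55 × 2 × 91 = 10,010 | 0 |

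**3. Can the group effect be estimated?** Take the usual linear predictor for a GEE or LMM, with G = 1 for Group 1:

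β0 + β1·G + β2·t + β3·G·t.

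Every available row has G = 1, so the columns for the intercept and G are identical, as are those for t and G·t. With three monthly points assumed, the design matrix has rank 2 of 4; with both arms it has rank 4 of 4. Only β0 + β1 and β2 + β3 can be estimated. The group effect β1 and the group-by-time effect β3 cannot. More tests per person do not change this, so repeated measures add no between-arm power for this outcome.

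**4. Possible alpha cost.** This applies only if the promised correction is an equal Bonferroni split over the two primaries, which the plan does not say. For the remaining outcome, by t-test with 55 per arm:

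| | alpha .05 | alpha .025 |
|---|---|---|
| Power at d = 0.65 | 92.2% | 87.0% |
| Detectable d at 80% power | 0.54 | 0.59 |

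**The case against.** The strongest points on the other side are these.

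- **Section I.13 writes no model and does not say the GEE/LMM is between arms.** True, and a GEE over time within Group 1 could be run. But two randomised groups, intention to treat, a sample size in units of d and an aim of increasing abstinence all imply a between-group contrast. A within-Group-1 trend has no control.
- **Group 2 might be tested somewhere.** Figure 2, which gives the assessment times, is not visible in the copy available here. Section I.4 also has the research assistant assess alcohol use at the randomization visit without naming a method. Neither shows follow-up breath tests in Group 2, and the text limits that arm to the surveys. The sentence about all participants using the device for the first time stands under the Group 1 heading.
- **The alpha cost is hypothetical and modest.** This stands. Even after the split, power at d = 0.65 is above 80%, and the detectable d stays below 0.65. The main defect does not depend on it.
- **Aim 1 can still be addressed by self-report.** This also stands, and the fix relies on it. But the plan does not make self-reported drinking the sole primary, and it defines the self-report outcome in two ways: days per week of use in Assessments, and "days/month of self-reported illicit drug use" in Section I.13.

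**Conclusion.** The concern holds and needs correcting before analysis. As written, one of the two primary outcomes in Section I.13 has about 9,900 scheduled observations in one arm and none in the other, and its treatment effect is not estimable at any sample size. The claimed gain in power is void for this outcome. The sample-size statement survives only for an outcome collected in both arms, which here means self-report.

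The conclusion rests on reading BAU and BAC as the same Soberlink test, on Group 2 having no breath testing outside the text, and on the GEE/LMM being meant to compare arms. The documents support all three. The count of tests further assumes 55 per arm and about 90 days. The fall in power from 92% to 87% further assumes a two-sided Bonferroni split.

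**What to change.** In both Assessments (Section I.4) and Section I.13:

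1. Name one primary between-arm outcome, measured the same way in both arms: TLFB days of alcohol use per 30 days at months 1, 2 and 3, tested at two-sided 0.05. State the single contrast to be tested across those months. Two-sided testing is an added choice, since the plan is silent.
2. Let this wording replace both present versions of the self-report outcome, including the reference to illicit drugs. If only the breath screen were deleted, illicit drug use would be left as the sole primary named in Section I.13.
3. Reclassify the Soberlink result as descriptive, Group 1 only: adherence to scheduled tests, percentage positive, and agreement with the TLFB.
4. Delete the breath screen from the sentence claiming greater power.

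The cost is wording in the protocol; no new data or patients are needed, provided the TLFB is among the assessments both arms complete, which should be stated. The drawback is that the comparison rests openly on self-report, and reporting may differ between arms because only Group 1 has its drinking checked.

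If the sponsor wants an objective primary, the alternative is the same alcohol test on the same schedule in both arms. That also removes the defect but needs extra resources and a change to what Group 2 undergoes.

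### Exclusion item 7 has its polarity reversed: as written, it excludes patients who have no current or pending legal action

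*Combined protocol and SAP*

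**What the plan says.** The eligibility rules stand in Section I, item 8 of the protocol. The exclusion list opens with "Exclusion Criteria: 1) Current suicide or homicide risk" and runs to eight items. The seventh reads "No course of current or pending legal action" and the eighth "8) Soberlink results being used for child custody or legal circumstance". The fifth also touches on legal exposure: "5) Unable to complete the study because of anticipated incarceration or move".

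The inclusion list has three items: a minimum age of 21, then "2) currently enrolled at Aware In home treatment, and 3) Primary or secondary DSM-5 diagnosis of alcoholism use disorder (AUD"). None concerns legal status. Section I, item 6 describes the population only as 110 people with DSM-5 alcohol use disorder recruited at the Aware facility.

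Under Section I, item 9, a trained and supervised research assistant assesses eligibility, and the result is reviewed with the project director or principal investigator before the patient starts.

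**The concern.** An exclusion list works in one direction: if the statement is true of the patient, the patient is out. Item 7 is true of a patient who has no legal matter. Followed to the letter, it keeps out the patients the trial appears to want and lets through, subject to the other criteria, only those it appears to want to keep out.

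Eligibility criteria fix the population to which the result applies, and they are the standard against which each enrolment is judged. If the list is followed exactly, the trial studies a population that nothing else in the protocol describes. If staff follow the apparent intent, each enrolled patient without legal action meets a written exclusion criterion. The sentence is the only statement of the rule, so the protocol offers no second wording to fall back on.

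**Working it through.** The plan gives no figure on this point, so there is none to reproduce. The check compares passages and applies simple set logic.

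**1. Is there a convention under which a negative wording states a requirement for entry?** Three other items are negatively worded. Items 3 and 4 read "3) does not have phone access with text message capabilities, 4) Unable to read or understand English", and item 5 begins in the same way as item 4. In each, the negative phrase names the disqualifying state: no suitable phone, no English, cannot complete. Items 1, 2, 6 and 8 also name disqualifying states. Item 7 would be the only one of the eight that has to be read against its heading.

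**2. Which patients are left?** Let L be the patients with current or pending legal action, and U those whose Soberlink results are used in a custody or legal matter.

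- Item 7 as written removes not-L, leaving L.
- Item 8 removes U, leaving not-U.
- Items 7 and 8 as written leave L and not-U: patients with legal action in which the device results play no part.
- With item 7 reversed, items 7 and 8 leave not-L and not-U.

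The two eligible sets have no patient in common, since one requires L and the other forbids it.

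**3. Which set fits the rest of the protocol?** Item 5 excludes people who expect incarceration, and item 8 excludes people whose results feed a legal matter. Both keep legal exposure out. The inclusion criteria and the population description contain nothing that would make legal action a condition of entry. All of this favours the reversed reading.

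**4. Is the rule repaired elsewhere?** The eligibility procedure (Section I, item 9) and the recruitment procedures (Section III, item 3) do not restate it. No other section does.

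**5. Illustration only: recruitment under the literal reading.** The share of patients with legal action, p, is not in the protocol. I assume p = 10% to 30%, full eligibility on the other criteria (including item 8) and full consent. Section I, item 4 gives 38 new patients a month and 300 current patients.

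- New intakes only: 38 × 0.10 = 3.8 and 38 × 0.30 = 11.4 a month. Then 110 / 3.8 = 28.9 months and 110 / 11.4 = 9.6 months.
- Counting current patients: 300 × 0.10 = 30 and 300 × 0.30 = 90. The remainder is 110 − 30 = 80 and 110 − 90 = 20. Then 80 / 3.8 = 21.1 months and 20 / 11.4 = 1.8 months.

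For comparison, under the reversed reading the current patients alone would supply 300 × 0.90 = 270 to 300 × 0.70 = 210 candidates, more than the 110 needed. The literal-reading range of about 2 to 29 months reflects the assumed share and whether the census is counted. It supports no conclusion about feasibility.

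**The case against.** The strongest reply is that this is a slip whose meaning can be recovered from the same sentence. Items 5 and 8 show the direction, the population is described without any legal condition, and a sensible assistant would read item 7 as intended. That stands as a statement about likely practice. It does not alter what the list says.

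A reader might go further than the documents allow in four ways.

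- *That the trial would in fact enrol only patients in legal proceedings.* Nothing suggests that anyone would apply item 7 literally.
- *That different assistants would read it differently and mix the sample.* This is possible, but Section I, item 9 requires review with the project director or principal investigator, which makes divergent readings less likely.
- *That the literal rule selects the patients with the strongest outside incentive to test negative or under-report.* Item 8 already removes those whose device results are used legally, and with them the most direct incentive. Some incentive may remain, but no passage supports ranking it.
- *That recruitment would fail.* The duration rests on an assumed share, and leaving out the 300 current patients lengthens it. Inclusion item 2 asks only for current enrolment, and flyers and clinicians reach existing patients. Section I, item 9 places interviews around admission, so use of that pool is plausible but not certain.

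It is also fair to say that the intended scope of item 7 is inferred. A corrected item would bar people in any legal matter, related to alcohol or not, and would overlap largely with item 8. That is a reason to ask the investigator before fixing the wording.

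**Conclusion.** The point holds. Item 7 is wrong as written under its heading: it conflicts with items 5 and 8 and with the described population, and no other part of the protocol corrects it. Taken with item 8, the literal rule defines a population that shares no patient with the one apparently intended.

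The practical harm is probably small, because staff are likely to read past the error and eligibility is reviewed a second time. What remains is a written eligibility rule that names the wrong population and that enrolments made on the apparent intent would not satisfy. The size in patients cannot be stated, since the share with legal action is not given. The sample size of 110, the power statement and the analysis plan are unaffected. The conclusion about the wording rests on no numerical assumption; the conclusion about intent is an inference from items 5 and 8 and needs the investigator's confirmation.

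**What to change.** The investigator should confirm what item 7 was meant to do and reconcile it with item 8. If the apparent intent is right, either of two one-line edits is enough: delete the leading negative so that exclusion 7 names the presence of a current or pending legal action, or move the item, as a statement that there is none, to the inclusion list. The same edit should say whether any legal matter counts or only certain kinds, and whether item 8 is still needed alongside it. Any screening form should be checked against the corrected wording; none is among the documents, so it should not be presumed wrong.

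The cost is an IRB amendment and, if needed, a change to the form. No sample size or analysis text has to change.
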